A sample protocol for this pilot study is shown in the Figure above. On Day 1 (lab visit #1) subjects will complete questionnaires, receive a wrist activity monitor, and a Personal Data Assistant (PDA; electronic diary) to record their daily pain, mood, sleep, and substance use (alcohol, caffeine, prescribed and over the counter medication, heating pads, ice packs, etc) while they sleep ad lib at home, following their usual sleep schedule. They will then undergo pain sensitivity testing (acute pain induction with forearm ischemia and heat, between noon-1pm as per our pilot). On Day 8 (lab visit #2) subjects will complete questionnaires, have their diaries and wrist actigraphy data reviewed and then will undergo pain sensitivity testing again. Following this subjects will be trained in home saliva collection, receive a kit to take home and will complete their saliva collection that night. The following morning (Day 9, home visit #1) two research staff (mixed gender team) will visit the subject in their home to set up and instruct the subjects in the bright light treatment, and collect their saliva kit and samples. Subjects will self-administer the bright light for 1 h/morning for 6 days before returning to the lab (Day 15, lab visit #3) for repeat questionnaires, review of their diaries and wrist actigraphy, pain sensitivity testing and issuing of the saliva collection kit. Research staff will again visit their homes to collect the saliva kit and samples (Day 16, home visit #2). After a further 7 days of bright light treatment, subjects will return for their last lab visit (Day 22, lab visit #4) for questionnaires, review of their diaries and wrist actigraphy, repeat pain sensitivity testing and issuing of the saliva collection kit. The following morning on Day 23 another home visit (home visit #3) will occur, and research staff will collect the light boxes, saliva kit, samples, and wrist monitors. The PDAs for electronic diaries will be left with the subject. During a 1 month follow up after cessation of the bright light treatment, subjects will continue to report their pain, mood and sleep once a day on the electronic diaries (once a day only to reduce burden and improve compliance). At the end of the follow up staff will collect the PDAs with electronic diaries during a final home visit.

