Bright Light Treatment At Home To Manage Chronic Pain In U.S. Veterans

NCT02373189

Document Date: 12/23/22

Data Analysis

Aim 1. To determine the feasibility and acceptability of bright light treatment in a sample of US veterans (n=30) experiencing chronic low back pain. For Aim 1 we will track the number of US veterans who express interest in the study, the number that meet our inclusion criteria, the number that enroll, the number of mornings that bright light is self-administered and the duration of the exposure, and we will collect treatment expectancy and treatment satisfaction ratings. Hypothesis 1: We expect reasonable feasibility in that (i) we will be able to enroll 2 US veterans per month, (ii) $\geq 75\%$ of those enrolled self-administer at least 30 mins of morning bright light on at least 50% of treatment days (this light should still be somewhat effective, as per winter depression studies [125, 126, 131]). Research Strategy Page 54 Contact PD/PI: [name] Hypothesis 2: We expect reasonable acceptability in that (i) at least 1 in 4 US veterans who are eligible for the study agree to participate, (ii) average expectancy rating at start of bright light treatment is $\geq 6/10$, (iii) the attrition rate is $\leq 30\%$, and (iv) average treatment satisfaction at end of bright light treatment is $\geq 6/10$. Aim 2. To examine the effects of 6 days and 13 days of bright light treatment on chronic pain intensity and sensitivity in US veterans (improved PTSD symptoms, mood and sleep are secondary outcomes).

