For Aim 2 we will plot daily diary ratings of pain intensity expressed as percentage change from baseline pain intensity (mean intensity over the 7 days of baseline). The point where the mean change for the whole sample achieves 30% (“moderately clinically meaningful effect” p.239, [137]) will reveal a potential candidate for an optimal treatment dose. We will also examine pain sensitivity (ischemia, heat) changes over the 4 lab visits. Hypothesis 3: We expect (i) a $\geq 30\%$ reduction in pain intensity ratings and (ii) a $\geq 30\%$ reduction in pain sensitivity (ischemia and thermal pain) by the 13th day of morning bright light treatment. As a preliminary analysis, we will examine these data with a within-subjects ANOVA to determine: a) effect size of change over 13 days of treatment; b) statistical significance of this change; c) whether there is significant non-linearity indicating that response to treatment reached a plateau. In an effort to understand a plateau effect, we will use a piecewise linear mixed model with a fixed change point occurring at the 30% change level. Random effects for time before the change point and time after change point will be included in the model. We will use graphical analyses to investigate violations of the model assumption. Secondary analyses for daily ratings of mood and sleep will be conducted similarly. For additional secondary analyses involving PTSD, depressive and anxiety symptoms, and sleep questionnaires, we will subject data to within-subjects ANOVAs to determine: a) effect sizes of changes over 13 days of treatment; b) statistical significance of these changes; c) whether there is significant non-linearity indicating that treatment response plateaued.

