Aim 3. To determine time course of decay of treatment response (decreased pain intensity) after cessation of light treatment. For Aim 3, we will plot daily diary ratings of pain intensity expressed as percentage change from the mean of pain ratings over the last 3 days of bright light treatment. The point where the mean change for the whole sample achieves 20% (less than a “moderate” decrease [137]) will reveal a potential candidate time for a maintenance dose of bright light. Second, we will subject these data to a within-subjects ANOVA to determine: a) effect size of erosion over 4 weeks of follow-up; b) statistical significance of this change. A change point modeling strategy similar to Aim 2 will be used here, but the change point will be set at a 20% level rather than a 30% level. Secondary analyses involving daily diary ratings of sleep and mood will be conducted as described above. Hypothesis 1: A mean increase of 20% in pain ratings is expected to occur within the first week post treatment (as per winter depression studies [125, 126, 131]). Hypothesis 2: Pain intensity is expected to return to baseline by 1 month post treatment (as per winter depression studies [125, 126, 131]).

We will also examine effects of other factors on treatment response. We will determine whether analyses must be adjusted for confounding factors including but not limited to age, BMI, race/ethnicity, employment, physical workload, any comorbidity (including depression and anxiety), history of traumatic brain injury, time from onset of chronic pain, current psychotropic and analgesic medications, and other treatments being received for chronic pain and/or PTSD. These analyses may involve treating these factors as time-varying covariates. We will also determine whether key factors moderate treatment response. We plan to test whether men or women

and those with low vs. high psychiatric symptoms (e.g., PTSD) show evidence of differential treatment response. These analyses will involve testing Sex or Psychiatric Symptom x Time interactions on pain intensity during and following treatment. In other exploratory analyses we will examine the correlations between change in DLMO and DLMO to midpoint of sleep interval and change in pain, mood and sleep.

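### The psychiatric-symptom moderator is framed as low versus high with no cut-point and no stated coding; if the score is split, this one secondary test loses roughly a quarter to more than half of its information.

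*SAP*

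**What the plan says.** The moderation plan is in the SAP's closing paragraphs, after Aim 3. It asks whether men and women differ in response and whether "those with low vs. high psychiatric symptoms (e.g., PTSD) show evidence of differential treatment response". The analysis is then described in one sentence: "These analyses will involve testing Sex or Psychiatric Symptom x Time interactions on pain intensity during and following treatment". No instrument, measurement time, cut-point or group size is given for the symptom variable, and PTSD is named only as an example.

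Three other places bear on the point.

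- SAP, Aim 1 sets the sample: "in a sample of US veterans (n=30) experiencing chronic low back pain". Hypothesis 2(iii) there accepts attrition of up to 30%.
- SAP, Aim 2 treats symptom measures as outcomes: "For additional secondary analyses involving PTSD, depressive and anxiety symptoms, and sleep questionnaires, we will subject data to within-subjects ANOVAs". That implies numeric scores.
- The Protocol section states "On Day 1 (lab visit #1) subjects will complete questionnaires", and questionnaires are repeated on Day 8. The light is set up on Day 9, so pre-light scores should be available, although the documents do not list which questionnaires are given at which visit.

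**The concern.** Psychiatric symptoms are set alongside sex, a genuine two-level factor, and are described in two levels. The within-subjects ANOVA used elsewhere in the SAP also takes a grouping factor readily. An analyst following the text could well divide the veterans into a low and a high group.

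That has two costs. First, a split treats everyone within a group as identical and treats people just either side of the cut as different, so the test loses power. Thirty people leave little to spare. Second, with no cut-point fixed, the cut can be chosen after the data are seen, and that choice can create or hide an interaction. What is at stake is the reading of one planned moderator analysis, which might influence who is studied next.

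**Working it through.** The documents give no power, alpha, cut-point or effect size for this test, so there is no stated figure to reproduce.

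**Inputs from the documents.** n = 30 (SAP, Aim 1). At the attrition limit, 30 × 0.70 = 21.

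**Assumptions, not in the documents.** Two-sided 5% test; linear moderation; correlation r between baseline score and individual pain change varied from 0.3 to 0.6.

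**1. Information kept by a split of a normal score.** If a share p is classed high, with cut c = z(1−p), the fraction kept is φ(c)² / [p(1−p)].

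- Median split: p = 0.5, c = 0, φ(0)² = 1/(2π), so the fraction is [1/(2π)] / 0.25 = 2/π = 0.637. The loss is 36.3%.
- Effective sample size: 30 × 0.637 = 19.1; 21 × 0.637 = 13.4.
- Unequal cuts: 40% high loses 37.8%; 33% high, 40.7%; 25% high, 46.1%; 20% high, 51.0%; 10% high, 65.8%.

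**2. Median split of other score shapes**, as 1 − corr(score, split)² on 10⁶ draws: uniform 25%; two moderately separated clusters 25%; chi-square with 4 df 45%; exponential 52%.

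**3. Power illustration.** 40,000 simulated bivariate-normal samples per row; continuous score against sample-median split.

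| n | r | Continuous | Median split |
|---|---|---|---|
| 30 | 0.3 | 37% | 24% |
| 30 | 0.4 | 61% | 41% |
| 30 | 0.5 | 83% | 61% |
| 30 | 0.6 | 96% | 80% |
| 21 | 0.3 | 27% | 18% |
| 21 | 0.4 | 45% | 29% |
| 21 | 0.5 | 67% | 44% |
| 21 | 0.6 | 85% | 63% |

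This tests one score against one change value per person. It is not a power calculation for the planned repeated-measures interaction on daily ratings.

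**4. Smallest detectable correlation at 80% power, continuous score.** By Fisher's z, r = tanh[(1.96 + 0.842)/√(n−3)]. At n = 30 this is tanh(2.802/5.196) = 0.49. With a median split, the table shows that r must be about 0.6 for the same power.

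**5. Effect of an open cut-point.** With no true moderation and n = 30, one pre-fixed median split rejects in 5% of samples. Taking the best of three cuts (lower third, median, upper third) rejects in about 12%. Searching every cut from the 20th to the 80th percentile rejects in about 27%. The continuous score stays at 5%.

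**The case against.** The strongest reply is that the SAP never commits to a split. The test it names is "testing Sex or Psychiatric Symptom x Time interactions on pain intensity"; the term is the symptom itself, not a symptom group, and it can be fitted with a continuous score. Low versus high may be only a verbal way of putting the question. This stands: the coding is left open, and the plan may already intend what is proposed here. It does not dispose of the point, because the text does not say so, and the same sentence settles both coding and cut-point.

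A reader might infer that the SAP specifies a median split and so discards a third of the study's information. The documents do not support that. They state no cut, and a clinical threshold fits the text equally well. The one-third figure needs a median split, a normal score and linear moderation, none of which is stated. Any loss falls on one moderator test; feasibility, pain response and decay after treatment are untouched.

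It is also fair to say that the power figures come from a simpler test than the planned one and use assumed correlations. At r = 0.3 the test is underpowered under either coding. The study is a pilot, and no hypothesis or success criterion depends on this moderator. Finally, a cut fixed in advance would answer the false-positive worry, though not the loss of information.

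**Conclusion.** The point holds in a limited form. The SAP frames the moderator as two groups and leaves both cut-point and coding open. If the score is split, the moderator test loses about 36% of its information under a median split of a normal score with linear moderation. Across the other shapes and cuts examined the loss runs from about 25% to more than 50%, so it is material for any plausible split. The power comparison shows the direction and rough size of the cost, not the power of the planned analysis. The false-positive inflation arises only if the cut is chosen from the data.

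This is a cheap improvement to a secondary analysis and does not threaten Aims 1 to 3. Even with a continuous score, 30 people give 80% power only for a correlation of about 0.5, so the result remains exploratory.

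**What to change.** Add a short statement to the SAP's moderation paragraph:

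- name the symptom scale or scales and the pre-light visit at which each is taken;
- enter the baseline PTSD and other symptom scores as continuous variables in the interaction with time;
- report the interaction estimate with its confidence interval;
- use low and high only to display predicted curves, for example at one SD below and above the mean.

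The cost is a sentence or two. No extra data collection is apparent, provided the relevant questionnaires are among those completed before the light starts, which the sponsor should confirm. The one statistical downside is the assumption of roughly linear moderation. A plot of individual pain change against baseline score can check it, in keeping with the graphical model checks already planned under Aim 2.
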